### **Objectives**

#### **A. Specific Aims**

Parental constraint of outdoor play may be fueling unhealthy emotional and physical development in today's children and adolescents. Time spent outdoors is a key determinant of unstructured play and overall physical activity levels, both of which are crucial to optimal development in youth. Modern barriers – such as crime, poor social ties among neighbors, and unsafe physical environments – constrain parental practices and reduce opportunities for outdoor play in children and youth. Low levels of perceived collective efficacy, a measure of perceived neighborhood cohesion and the collective capacity to solve neighborhood problems, has been proposed as a social environmental factor that constrains outdoor play by parents either attempting to avoid potentially dangerous situations or using defensive behavior by upgrading security measures. Moreover, incivilities in the neighborhood physical environment (e.g. litter, graffiti, blighted property) may influence parents' perceived collective efficacy. Consequently, a child's ability to achieve the recommended minimum of 60 minutes of daily physical activity may be limited by a complex interaction between neighborhood social and physical environmental factors and the extent to which parents respond by constraining offspring outdoor play. The central hypothesis of this research is that modifiable factors in the neighborhood social and physical environment result in parental constraint of offspring outdoor play, which reduces overall physical activity during critical years of development. This research will use qualitative methods to generate a comprehensive understanding of how and which environmental factors play a crucial role in parental constraint of outdoor play and promote low levels of within-neighborhood physical activity. This ancillary study will recruit 32 parents/guardians of participants from the parent study, Translational Investigation of Growth and Everyday Routines in Kids (TIGER Kids) Study (USDA 3092-51000-056-04A), to participate in in-depth interviews. My ultimate goal is to use knowledge gained from this ancillary study to generate community-based interventions that will target neighborhood factors to successfully reduce parental constraints on outdoor play.

The aims of this ancillary study are:

**Aim 1:** Implement qualitative methods (in-depth interviews) among parents/guardians living in varied neighborhood environments (low/high incivilities) to gain in-depth information and perspectives of the social environment's influence on constrained outdoor play practices.

[figure not shown]
**A1a.** Identify how parents/guardians experience neighborhood incivilities and whether/how incivilities influence perspectives shared during in-depth interviews (Aim 1).

## B. Background

Play is so important to optimal child development that it has been recognized by the United Nations High Commission for Human Rights as a right of every child. The neighborhood environment has become an important setting to achieve outdoor play, since time for free play has decreased during school hours. Today's youth spend too little time playing outdoors, contributing to overall low levels of physical activity which has been linked to obesity, cardiometabolic risk and unhealthy development. Neighborhood environmental factors may contribute to low levels of physical activity; however, results have been inconsistent. These inconsistencies are due in part to (1) "conceptual mis-match" between environmental characteristics and physical activity domains (e.g., relating total physical activity, instead of within-neighborhood physical activity, to neighborhood characteristics) and (2) failure to examine mediators/moderators of environment-physical activity relationships such as parenting behaviors. Perceived collective efficacy, which is a social environmental measure of social cohesion and control among neighbors, may influence physical activity opportunities for adults and children. For children and adolescents, parents may constrain their child's outdoor play in part because of their sense of collective efficacy (Figure 2). My dissertation work suggests that this relationship may be modified by incivilities in the neighborhood physical environment, where, for example, graffiti and blighted property in the neighborhood exacerbate the problem. This ancillary study will use qualitative methods to gain

an in-depth understanding of the social environment's influence on parental constraint of outdoor play.

**Figure 2:** Conceptual Framework for the Proposed Research

**Significance:** This ancillary study will be performed among parents/guardians living in two distinct neighborhood types (low vs. high incivilities) to further understand how social environments and processes may differ across varied physical environments. This study is significant because although

childhood obesity and unhealthy development are common, research exploring environmental influences on physical activity-related parenting behaviors is scarce, and the proposed pathway has not been explored in children or adolescents using qualitative methods. Thus, the results will inform community-based interventions that target modifiable social and physical environmental factors to increase neighborhood physical activity thereby promoting the healthy development of children and adolescents.

**Innovation:** This study is innovative in its scientific questions and hypotheses, which hold promise to shift the paradigm by focusing on the environmental triggers that may promote or impede children's physical activity. If parental constraint of outdoor play is the mechanism by which aspects of the neighborhood physical and social environment influence offspring's within-neighborhood physical activity, then interventions can be designed to address parent-imposed barriers to outdoor play.

## **Inclusion and Exclusion Criteria**

This ancillary study will include 32 parents/guardians of TIGER kids participants who previously completed the parent study baseline (Y0) visit. Any parent/guardian of a TIGER Kids participant who completed baseline measurements is eligible for this ancillary project.

### **Inclusion Criteria:**

- Child completed baseline measures (Y0) for the TIGER Kids Study.

### **Exclusion Criteria:**

- Child did not complete baseline measures (Y0) of the TIGER Kids Study.
- Did not report a home address at the baseline (Y0) TIGER Kids study visit.
- Unwilling or unable to participate in an in-depth interview.

In addition to the exclusion criteria listed above, participants who refuse to sign an informed consent document will be excluded from the study. Consent will be obtained upon each participant's arrival at the Pennington Biomedical Research Center or community location [i.e. YMCA or East Baton Rouge Parish Library (EBPL) Branch] before participating in the in-depth interview. Furthermore, the principal investigator has the right to withdraw a participant from the study at any point for any reason.

## **Number of Subjects and Subject Timeline**

32 parents/guardians of participants from the TIGER Kids parent study will be recruited for this ancillary study. All parents/guardians will be recruited after their child has completed the baseline (Y0) TIGER Kids study visit. Recruitment will begin July 1, 2017 and be completed by July, 2018.

## **Recruitment Methods**

Parents/guardians will be recruited from the existing participants in the TIGER Kids parent study. Recruitment of parents/guardians will occur after the child has complete baseline (Y0) measures of the parent study. Contact information obtained from those who have already completed the baseline visit of the TIGER Kids parent study will be used to recruit for this ancillary study in-depth interviews. Furthermore, baseline data from the Y0 TIGER Kids study visit on socio-economic status, race, and neighborhood environment will be used to recruit parents from diverse demographic backgrounds and two distinct neighborhood environments (low vs. high incivilities). Consent will be obtained when the parent/guardian comes to Pennington Biomedical for their in-depth interview.

## **Study Timelines**

Enrollment is currently underway for the TIGER Kids parent study, and will continue through March, 2018. Data collection for the two time-points of the parent study will continue through August 2019, however only baseline data from the parent study will be used for this ancillary study. The investigators estimate all baseline visits for the parent study will be completed by March 2018. Recruitment of parents/guardians for this ancillary study will be completed by July, 2018. All data collection will be completed by December, 2018.

**Table 1: Two-year Study Timeline (Projected Start Date: July 2017)**

	2017		2018				2019	
	Q3	Q4	Q1	Q2	Q3	Q4	Q1	Q2
Parent Study Recruitment and Y0 visits (ongoing since June 2016)								
Ancillary Study Recruitment								
Ancillary Study Data Collection (In-depth Interviews)								
Ancillary Study Data Analysis								
Ancillary Study Manuscript Development and Submission								

### **Consent Process**

For this ancillary study, informed consent will be obtained from the parent/guardian of the TIGER Kids study who is willing to participate in in-depth interviews. Written informed consent will be collected in a private room located in Pennington Biomedical Research Center or a community location (i.e. YMCA or EBRPL branch) during the study visit at which the in-depth interview will take place. This visit will be a separate visit and subsequent to the parent study (TIGER Kids) Y0 baseline study visit. The study procedures will be explained to parent/guardian. They will be asked if they have any questions about the study and will be given adequate time to review and ask questions.

### **Study Endpoints**

There is no primary endpoint this study. This study is qualitative and therefore aims to gather in-depth information from the participant to understand how the neighborhood environment may or may not impact their parenting decisions regarding their child's outdoor play.

### **Procedures Involved**

**Study Design:** The overall strategy is to implement in-depth interviews among 32 parents/guardians of participants from the TIGER Kids Parent Study (USDA 3092-51000-056-04A). This ancillary study will be implemented among 32 parents/guardians from diverse neighborhood environments using purposeful sampling. We anticipate that a sample of 32 parents/guardians will be sufficient to reach saturation.

**Qualitative Measurements:** Semi-structured in-depth interviews will be conducted among TIGER Kids parents/guardians stratified by neighborhood environments (low and high incivilities). An interview protocol will be developed in collaboration with an expert in qualitative research ([name], project consultant). Interviewees will sign informed consent prior to data collection. Individual interviews will last approximately 1.5 hours including time for participants to complete a short demographic survey. Participants will receive an incentive of \$25 for interview completion. All interviews will be taped and transcribed verbatim.

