### **Data Analysis Plan**

For this ancillary study, all transcribed interview data will be imported into the appropriate qualitative data software (e.g. NVivo10). One interview will be chosen for two trained staff members to code and establish an initial code-book. All coding discrepancies will be discussed until an initial codebook detailing code definitions is agreed upon. An additional interview will then be coded by two staff members to refine the codebook and inter-rater reliability will be calculated. Once a final coding protocol is established, all remaining interviews will be coded. A thematic analytic approach will be used to analyze participant responses within coded text segments for similarities and differences that

clustered to classify emerging themes. All themes will be recorded in Microsoft Excel, and similar themes may be further grouped into broader thematic categories if necessary. Concise phrases that capture the overall meaning will be assigned to each theme. Themes will be sorted and compared between participants grouped in low vs. high incivility neighborhoods to determine if differences in responses between the two groups were present (Aim 1a).

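### Aim 1a compares themes by a neighborhood-level label, but the plan neither spreads parents across neighborhoods within each incivility group nor counts how many neighborhoods a theme comes from

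*Combined protocol and SAP*

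**What the plan says.** The sampling statement in Procedures Involved is "This ancillary study will be implemented among 32 parents/guardians from diverse neighborhood environments using purposeful sampling". The same section stratifies the interviews by low and high incivilities and supports the sample size with "We anticipate that a sample of 32 parents/guardians will be sufficient to reach saturation". It gives no number per stratum.

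Recruitment Methods says how parents are chosen: "baseline data from the Y0 TIGER Kids study visit on socio-economic status, race, and neighborhood environment will be used to recruit parents". The aim there is a demographic mix and two neighborhood types.

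The Inclusion and Exclusion Criteria admit any parent or guardian of a child with baseline measures. One exclusion is "Did not report a home address at the baseline (Y0) TIGER Kids study visit", so every participant has an address on file.

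For Aim 1a, the Data Analysis Plan has themes "compared between participants grouped in low vs. high incivility neighborhoods", to see whether responses differ between the two groups. The analysis has no step at the level of the individual neighborhood.

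**The concern.** The grouping variable in Aim 1a describes a place. Parents from the same streets carry the same label and may also share the same blight, the same neighbors and the same incidents. To credit a difference in themes to the level of incivilities, one wants to see it recur in several places at that level. A single incident or one active neighborhood association, described by several neighbors, could appear as a repeated theme in one group and not in the other.

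The Specific Aims say the findings are meant to shape community interventions aimed at neighborhood factors. If the circumstances of one place were taken for a feature of high- or low-incivility neighborhoods in general, those interventions could be aimed at the wrong thing. The spread of parents across places is fixed once the interviews are done. The count of places behind each theme can be made at any time while addresses are held.

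**Working it through.** No figure in the plan can be reproduced here. The 32 rests on expected saturation, and Study Endpoints states that there is no primary endpoint. The check is therefore a reading of the sections side by side, followed by a short illustration.

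**1. Where the label sits.** Recruitment Methods, Procedures Involved and the Data Analysis Plan all attach low/high incivilities to the neighborhood.

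**2. What controls selection.** Recruitment Methods names socio-economic status, race and neighborhood environment, the last as two types. The eligibility criteria limit neither parents per neighborhood nor parents per household. The reference to diverse environments in Procedures Involved points toward spread but carries no rule. A group drawn from two neighborhoods could meet every written criterion.

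**3. What the analysis does.** It compares participants by group. It does not ask how many distinct neighborhoods lie behind a theme.

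**4. What would make such a count possible.** Baseline home addresses are held for all participants. However, the plan does not name the geographic unit on which incivilities are rated, and that unit is needed to decide who shares a neighborhood.

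**5. Illustration only.** Assume an even split, 32/2 = 16 per group (not stated in the plan), with *m* parents from one neighborhood who all raise a theme that nobody else raises. That place supplies *m*/16 of the group:

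| *m* | Share of group |
|---|---|
| 1 | 1/16 = 6.25% |
| 2 | 2/16 = 12.5% |
| 4 | 4/16 = 25% |
| 8 | 8/16 = 50% |

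A design-effect calculation is also possible. The effective number per group is 16/(1 + (*m* − 1)ρ), where ρ is the within-neighborhood correlation:

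- *m* = 4, ρ = 0.1: 16/1.3 = 12.3
- *m* = 4, ρ = 0.3: 16/1.9 = 8.4
- *m* = 2, ρ = 0.1: 16/1.1 = 14.5
- *m* = 2, ρ = 0.3: 16/1.3 = 12.3

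Group size, *m* and ρ are all assumed. The two illustrations also describe different situations: a theme raised by everyone in one place and by nobody elsewhere has no variation within places, which corresponds to ρ = 1, not 0.1 to 0.3. Neither set of figures estimates what will happen in this study, and the point does not depend on them.

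**The case against.** The strongest reply has four parts.

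- **The subject is the parent's experience.** The Specific Aims speak of perceived collective efficacy, Aim 1a asks how parents experience incivilities, and Study Endpoints refers to parenting decisions. Two neighbors who respond differently are informative and are not mere duplicates. This stands, and it rules out the stronger reading that the neighborhood is the only unit of Aim 1a. It does not remove the need for recurrence across places when a group difference is credited to the label.
- **Clustering is not shown.** The documents give no spread of addresses, and purposeful sampling with diversity in mind leans toward spread. This also stands. A reader might infer that parents will in fact be concentrated in a few places; the documents do not support that.
- **Effective sample size belongs to a different kind of study.** There is no test, no prevalence estimate and no rule that counts decide a difference. This stands, and it is why the figures above are illustration only.
- **Coders would notice.** With verbatim transcripts of long interviews, several parents describing the same incident may well be recognized. That is plausible, but it relies on alertness, and the plan has no step that requires it.

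**Conclusion.** The concern holds in a limited form. Aim 1a compares participants by a neighborhood-level label, and the text available for review contains neither a rule that spreads parents over distinct neighborhoods within a group nor a check on how many neighborhoods a theme comes from. A theme local to one place could therefore be read as an incivility difference, if several parents turn out to share a neighborhood.

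Two stronger conclusions might be drawn, and neither is supported. One is that the comparison is statistically invalid or inflates an error rate; the study makes no formal test. The other is that a fixed cap per neighborhood is required; the documents give no basis for any particular number, and a cap cannot be applied until the neighborhood unit is named.

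The size of the problem is unknown, because the number per group, the number of parents per neighborhood and the similarity of neighbors' accounts are not given. This is a low-cost improvement to what Aim 1a can conclude. It is not a flaw that undermines the study.

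**What to change.** **Data Analysis Plan.** Name the geographic unit on which incivilities are rated. Using the baseline home addresses and that unit, record for each theme, within each incivility group, the number of distinct neighborhoods as well as the number of parents. Report a theme found in only one neighborhood as a local finding and not as a difference between incivility groups. Give the total number of neighborhoods per group, so that the reader can see how many places the comparison rests on.

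**Recruitment Methods and Procedures Involved.** Add that, when otherwise suitable parents are available, one from a neighborhood not yet sampled is preferred. This is a preference, not a cap, so it cannot block recruitment when few parents fit the wanted combination of incivility level, socio-economic status and race.

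**Cost.** One more column in the theme table, one sentence in recruitment, and slightly less freedom in choosing parents. No new data are needed on participants, since the addresses are already held. Single-neighborhood themes are still reported, under a different description. The analysis part is useful even if recruitment is left as it is.

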### **Data Analysis Plan**

For this ancillary study, all transcribed interview data will be imported into the appropriate qualitative data software (e.g. NVivo10). One interview will be chosen for two trained staff members to code and establish an initial code-book. All coding discrepancies will be discussed until an initial codebook detailing code definitions is agreed upon. An additional interview will then be coded by two staff members to refine the codebook and inter-rater reliability will be calculated. Once a final coding protocol is established, all remaining interviews will be coded. A thematic analytic approach will be used to analyze participant responses within coded text segments for similarities and differences that

clustered to classify emerging themes. All themes will be recorded in Microsoft Excel, and similar themes may be further grouped into broader thematic categories if necessary. Concise phrases that capture the overall meaning will be assigned to each theme. Themes will be sorted and compared between participants grouped in low vs. high incivility neighborhoods to determine if differences in responses between the two groups were present (Aim 1a).

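### Does the Aim 1a comparison of low- and high-incivility neighborhoods need a stated number of interviews and a saturation check in each group?

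*Combined protocol and SAP*

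**What the plan says.** The Procedures Involved section sets the sample: "This ancillary study will be implemented among 32 parents/guardians from diverse neighborhood environments using purposeful sampling". It then justifies the number: "We anticipate that a sample of 32 parents/guardians will be sufficient to reach saturation". The next paragraph of that section says the interviews are "stratified by neighborhood environments (low and high incivilities"). Recruitment Methods adds that baseline data from the parent study will be used to "recruit parents from diverse demographic backgrounds and two distinct neighborhood environments (low vs. high incivilities").

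The Data Analysis Plan describes a thematic analysis of coded text. Similar themes may be merged into broader categories. The last step serves Aim 1a: "Themes will be sorted and compared between participants grouped in low vs. high incivility neighborhoods", the purpose being "to determine if differences in responses between the two groups were present (Aim 1a").

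The total of 32 appears in several sections. In the text available for review, no section gives the number per neighborhood type, an allocation ratio, a saturation criterion within each type, or a rule for reading a theme that only one group voices. Study Endpoints states: "There is no primary endpoint this study".

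**The concern.** The sample size sentence speaks of 32 parents as one sample, but Aim 1a splits them in two. Saturation in the whole sample does not guarantee saturation in each part, because each part is smaller. If few parents hold a theme, it may be voiced in one group and by chance not in the other, although it is equally common in both. An analyst who took that pattern at face value would report a neighborhood difference that does not exist.

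The contrast is a declared aim, and the protocol intends the results to inform community-based interventions, so a false contrast would not be harmless. The problem would grow if recruitment gave very unequal groups, which nothing in the text rules out. The plan's verb for the comparison, to determine, also sounds firmer than a small qualitative sample can support.

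**Working it through.** **Inputs.** From the documents: 32 interviews in total, two strata, and no stratum sizes. Assumed, because the documents give no figures: theme prevalence *p* from 5% to 30%, the same in both strata; splits of 16/16, 20/12 and 24/8; independent interviews; every voiced theme coded.

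**The plan's own figure.** The 32 comes with no prevalence, target probability or saturation rule. No formula can reproduce it, and none can show it wrong.

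**Step 1: hearing a theme at least once.** With *q* = 1 − *p*, the chance in *n* interviews is 1 − *q*^*n*. For *p* = 0.10:

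- *n* = 32: 1 − 0.9^32 = 96.6%
- *n* = 16: 1 − 0.9^16 = 81.5%
- *n* = 8: 1 − 0.9^8 = 57.0%

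Pooled coverage is therefore better than coverage within a stratum, as the concern says.

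**Step 2: hearing it in one stratum only.** For strata of size *a* and *b*, the chance is (1 − *q*^*a*)*q*^*b* + (1 − *q*^*b*)*q*^*a*. At 16/16 and *p* = 0.10, *q*^16 = 0.185, so the chance is 2 × 0.815 × 0.185 = 0.302.

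| Prevalence in both strata | 16/16 | 20/12 | 24/8 |
|---|---|---|---|
| 5% | 49.3% | 51.1% | 56.8% |
| 10% | 30.2% | 33.5% | 44.2% |
| 15% | 13.7% | 17.0% | 28.2% |
| 20% | 5.5% | 7.9% | 17.1% |
| 30% | 0.7% | 1.5% | 5.8% |

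At 16/16 the chance falls below 10% once prevalence passes about 17%.

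**Step 3: what such a theme looks like.** At 16/16, given that a theme is heard in one stratum only, the number of parents voicing it follows Bin(16, *p*) restricted to at least one. The chance that it is only one or two parents is 92% for a 5% theme and 74% for a 10% theme. Most spurious contrasts would thus be visibly thin.

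**Step 4: a spurious contrast that looks solid.** The chance of three or more voices in one stratum and none in the other is *q*^*b* · P(Bin(*a*, *p*) ≥ 3) + *q*^*a* · P(Bin(*b*, *p*) ≥ 3). Its maximum over all *p* is 7.9% at 16/16 (near *p* = 0.11), 10.8% at 20/12 and 20.6% at 24/8. The reassurance is good for an even split and weaker for a very uneven one.

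**The case for a change.** The strongest case for a change is that saturation is the plan's own criterion, and that it should hold at the level where the plan compares. Naming 16 per group, logging new codes in interview order and judging saturation by group would need no extra interviews. Without that, a reader cannot tell a neighborhood contrast from a theme that too few interviews missed. At 24/8 even a 20% theme would appear in one group only 17% of the time.

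The facts behind this stand: stratum sizes and the level of saturation are not written down. Three points limit what follows.

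- The sample size sentence does not confine saturation to the pooled sample. It is silent on the level, and the stratification is described in the next paragraph, so the number may have been chosen with the two groups in mind.
- A split as uneven as 24/8 has no basis in the documents. Recruitment uses baseline data to find parents in both neighborhood types, which gives the team control over the balance.
- The binomial model fits poorly. Sampling is purposeful and interviews are semi-structured, so a parent's chance of mentioning a theme is not one fixed value. The option to merge similar themes also tends to yield broader and more prevalent categories, where the table shows little effect. That helps only in part, since merging is optional.

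Some of the possible remedies are matters of preference. Counting parents per theme is a choice on which qualitative analysts reasonably differ. Labelling a contrast exploratory separates little in a study without confirmatory claims, and softening one verb changes wording, not analysis.

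**Conclusion.** No change to the plan is needed. The plan leaves out a detail that analysts can fill sensibly; it does not prescribe an analysis that gives a wrong answer. It contains no presence-or-absence rule, makes no inferential claim, and already recruits from both neighborhood types.

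The size depends on assumptions. With equal prevalence, independent interviews and 16 per group, a one-group-only theme arises by chance in about 30% of cases at 10% prevalence, 5.5% at 20% and 0.7% at 30%. The effect is thus confined to uncommon themes, unless the split turns out very uneven. When it does arise at 16/16 for themes held by 5% to 10% of parents, only one or two parents voice the theme in 74% to 92% of cases, and an experienced analyst would not build a neighborhood difference on that. The actual group sizes will be known when the results are written up, and a reader can weigh the Aim 1a contrasts against them then.
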